9.0 STUDY TREATMENTS

9.1. Description of Investigational Product

Group-I: Test

Name: Beclomethasone Dipropionate Metered Dose Inhaler (Inhalation Aerosol) (0.04 mg/ INH);

Manufactured by: Aurolife, a subsidiary of Aurobindo Pharma, USA, Inc., [name].

Group-II: Reference

Name: QVAR[®] 40 mcg (Beclomethasone dipropionate hydrofluoroalkane), Inhalation Aerosol;
Manufactured by: Teva Pharmaceuticals LLC Frazer, PA 19355.
NDC code: 59310-202-12

Group-III: Placebo

Manufactured by: Aurolife, a subsidiary of Aurobindo Pharma, USA, Inc., [name].

Subjects will receive one inhalation (0.04 mg/ INH) of Study medication (Test/ Reference/ Placebo) twice daily.

9.2. Investigational product Administration

As per randomization schedule, subjects will be randomized to either the Test or Reference or Placebo in 2:2:1 ratio.

Instructions for Use

There are 2 main parts of your inhaler including the:

- Metal canister that holds the medicine (See Figure A)
- Plastic actuator that sprays the medicine from the canister (See Figure A)

[figure not shown]

Figure A

- The inhaler has a protective dust cap that covers the mouthpiece of the actuator (See Figure A). The protective dust cap should be removed before use.
- The inhaler comes with a dose counter located on the back of the actuator (See Figure B). The dose counter window will show you the number of actuations (puffs) of medicine remaining in units of 2. The inhaler contains “120” actuations (puffs).

[figure not shown]

Figure B

- The first time you use inhaler, the dose counter will show “120” actuations remaining (See Figure B). Each time you press the metal canister, a puff of medicine is released and the dose counter will count down.
- When the dose counter reaches 0, it will continue to show 0 and you should replace your inhaler.
- The dose counter cannot be reset and is permanently attached to the actuator. Never change the numbers for the dose counter or touch the pin inside the actuator

Do not remove the metal canister from the plastic actuator.

Before using your inhaler:

Remove the cap from the mouthpiece of the actuator (See Figure C). Check the mouthpiece for objects before use. Make sure the metal canister is fully inserted into the actuator.

[figure not shown]

Figure C

Priming your inhaler:

Before you use your inhaler for the first time or if you have not used your Inhaler for more than 10 days, you will need to prime your Inhaler.

- Before priming, the inhaler will show a black dot in the dose counter window (See Figure D).

[figure not shown]

Figure D

- Hold the Inhaler in the upright position and with the mouthpiece pointing away from you.
- Press down on the metal canister 2 times and release 2 actuations (puffs) into the air and away from your face.
- After priming 2 times, the dose counter should read “120.”

Your Inhaler is now ready to use.

Using your inhaler:

Step 1: Remove the cap from the mouthpiece of the actuator (See Figure C). Check the mouthpiece for objects before use. Make sure the metal canister is fully inserted into the actuator.

Step 2: Breathe out as fully as you comfortably can. Hold the inhaler in the upright position (See Figure E). Close your lips around the mouthpiece, keeping your tongue below it.

[figure not shown]

Figure E

Step 3: While breathing in deeply and slowly, press down on the metal canister with your finger (See Figure E). When you have finished breathing in, hold your breath as long as you comfortably can (5 to 10 seconds).

Step 4: Take your finger off the metal canister and remove the inhaler from your mouth. Breathe out gently.

After using your inhaler:

- Replace the cap over the mouthpiece right away after use.
- You should rinse your mouth with water after you finish using inhaler.
- Clean the mouthpiece of your inhaler weekly with a clean, dry tissue or cloth.
- Do not wash or put any part of your inhaler in water¹⁰.

9.3. Packaging and Labeling of Study drug

Packaging and labeling of study medication will be conducted as per applicable regulations by the third party. Study medication will be supplied by Aurobindo Pharma Ltd to the third party service provider engaged for randomization and drug supply management.

9.4. Randomization

This will be randomized and double blind study. The actual treatment given to individual subject will be determined by a randomization scheme prepared by third party. Randomization will be done after completion of placebo run in period.

An IWRS (Interactive Web Response System) will be used to administer the randomization schedule. The programming, validation and monitoring of the randomization process by IWRS will be guided by the applicable SOPs of the IWRS vendor. In practice, the investigator or designee will use the IWRS system to receive the dosing formulation (test/reference/ placebo) for the subject.

A computerized randomization code will be generated by third party or designate, appropriate to the study design.

A third party or designate will provide password protected study randomization code via a secure file transfer procedure prior to the start of the study to the IWRS vendor. Only those individuals performing investigational medicinal product dispensing/ reconciliation activities are to have access to the randomization code. No further distribution of the randomization code to individuals not involved in dispensing the investigational medicinal products is permitted without proper documentation and rationale. If the randomization is maintained in paper format (i.e. hard copy), it will be retained with limited access under lock and key. Study participants will be aware that they will receive different formulations of a same drug without being informed which product (Test or Reference or Placebo) is being administered. Furthermore, the randomization code will not be available to the physician and nursing staff involved in the collection, monitoring, revision, or evaluation of adverse events or to clinical staff who could have an impact on the outcome of the study.

The randomization code must not be broken except in emergency situations for which the identification of the study treatment of a subject is required by the Qualified Investigator to complete a serious adverse event report or the clinical report. In such situations, the randomization information will be accessed through IWRS by the designated individual(s) pharmacist, and the date and reason for breaking the blind must be recorded.

Biostatistics group or designate will release the randomization code to designated study team members following the release of the study data. The randomization code will be used for subject assignment to treatment and for statistical and reporting purposes.

Screening number assigned to a study subject will remain the same throughout the study. The subjects may participate in the study only once and discontinued subjects must not be re-enrolled. If subject withdraws consent after randomization allotted or does not receive study treatment for any reason, the randomization number will not be re-used.

No member of study site or the study team will have access to randomization code until completion of the study statistical analysis.

Subject Identification Code Numbering System

Once a subject's eligibility criteria is satisfied, the subject will be assigned with screening number, starting with three digit site number followed by three digit subject number (e.g., 201001) in chronological order of enrollment in each site. The Investigator will issue the Study Drug to the subject as per IWRS method. If subject discontinues the study, the subject number will not be reused, and the subject will not be allowed to reenter the study.

9.5. Masking and Unmasking

This is a Randomized, Multiple-dose, Double-blind, Placebo Controlled, Parallel group and Multicentric study. It will be ensured that neither subject nor investigator/research team can differentiate between test, reference and placebo. The treatment each subject will receive will not be disclosed to the investigators, study center personnel, subject, sponsor, or AXIS staff involved in the study conduct, monitoring, data review or analysis. The treatment codes will be held by the independent third party.

Neither any member of study site nor the study team will have access to randomization code until completion of the study and database lock.

9.6. Treatment Compliance

Compliance will be assessed by subject diary and inhalation records of study medication. This will be recorded in the CRF/ eCRF.

Treatment compliance will be assessed on the basis of diary cards with following formula

$$\frac{(\text{Number of doses administered}) \times 100}{\text{Number of expected doses}}$$

Compliance will be presented as subjects who have taken approximately 75% to 125% of the doses of the assigned study drug and completed the evaluation within the designated visit.

Example: If subject received 18 doses of study medication and discontinued from study on day 11. Study medication needs to be taken twice daily for 28 days, hence the expected number of doses would be 56. Treatment Compliance = $18/56 \times 100 = 32.1\%$.

9.7. Prohibited Medications

During the study no other asthma medication will be allowed except investigational product and Salbutamol rescue inhalation. Due to the nature of the study and the Test product, certain medications which may interfere with the interpretation of the study results are prohibited 04 weeks before study enrollment as well as during the course of the study. These are outlined below:

1. β 2 Blockers
2. Anti-arrhythmics, anti-depressants, MOA inhibitors
3. Inhaled or other forms of Corticosteroids, LABA
4. Anticholinergics, Anti-histamines, Nedocromil, Sodium Cromoglycate, Leukotriene antagonists, Xanthine derivatives, Ephedrine.

9.8. Study Drug Accountability

Study medication will be provided by the Sponsor to the investigators through a third party packaging vendor. Study medication shall be kept under controlled access i.e., locked area with restricted access at investigator site and will be supplied only to suitable subjects under the responsibility of investigator/ study personnel. Study medication shall be stored under specified storage conditions as mentioned in the IP label. Investigator/ Study personnel will receive study medication and will document the same in applicable documents.

A record of study medication dispensed to trial subjects and returned shall be appropriately documented in IP logs provided by Axis/ third party.

At the end of study or in between if required investigator will return the used/ unused/ expired/ defective/ empty/ partially used study medication to third party and will document the same. Study medication can be destructed at site as per applicable regulations in presence of authorized study personnel and certificate for destruction shall be obtained and filed in Trial Master File and copy in Site Master File.

Investigator, a member of the investigational staff, or a hospital pharmacist must maintain an adequate record of the receipt and distribution of all study drugs using the IP Accountability Forms. These forms must be available for inspection at any time.

10.0 STATISTICS AND DATA COLLECTION

A general description of the statistical methods to be used to analyze the data is outlined below. Specific detailed description of analyses including list of displays will be provided in the Statistical Analysis Plan which will be finalized before clinical study data base lock. Data management plan will be prepared and finalized before data base designing.

General Analysis Considerations

Continuous data will be described using non-missing observations (n), Mean, Standard Deviation, Median, Minimum and Maximum values. Categorical data will be described using counts and percentages. Analyses will be performed using SAS version 9.2 or above.

Unless specified otherwise, all statistical testing will be two-sided and will be performed using significance (α) level of 0.05.

This study will be double blind randomized parallel group study with three arms: Reference Formulation, Test Formulation, Placebo formulation. Randomization will be in 2:2:1 proportion. The potential total enrolled sample size will be 1550 subjects [(620 (Test): 620 (Reference): 310 (Placebo)]. The subjects will be assigned to the placebo or active groups as per a predetermined randomization schedule. Randomization schedule will be generated using appropriate software package.

10.2. Subject Disposition

Number of subjects screened, entered run-in period, randomized, completed and discontinued will be presented along with reasons for screen failure and study discontinuation. Number of subjects assigned to various analysis populations will be presented. Reasons for exclusions from mITT and PP population will be listed by subject.

10.2.1. Safety Population

The Safety population will include all randomized subjects who received at least one dose of investigational study treatment during double blind treatment period.

10.2.2. mITT Population

The mITT population will include all randomized subjects who meet all inclusion/exclusion criteria, receive study treatment, and have at least one post baseline efficacy assessment. If subject discontinued due to lack of efficacy and does not have a post baseline value, then subject will be included in mITT population with baseline value carried forward. Missing efficacy results in the mITT population will be imputed using last observation carried forward (LOCF). The mITT population will be used to compare both test and reference products for superiority over placebo.

10.2.3. Per Protocol Population

The PP population will include all randomized subjects who meet all inclusion/exclusion criteria, are found to be compliant with the assigned study treatment, who return to the study site for the primary endpoint visit at 4 weeks (+/- 2 days) OR discontinue from the study as a treatment failure, and do not have any major protocol deviation impacting efficacy outcome. The PP population will be used for the bioequivalence evaluation of test vs. reference. Subjects who

used at least 75% and no more than 125% of study treatment doses will be considered to be compliant to study medication. Compliance will be assessed based upon diary data for study drug administration. Protocol deviations will be classified as major (impacting efficacy assessment) or minor, prior to database lock using blinded study data by study personnel who are not aware of treatment assignments. Protocol deviation classification and individual subject's assignment to analysis population will be finalized before unblinding of data. Summary of subjects with Major vs. Minor Protocol deviations will be provided along with listing.

Subjects discontinued early for reasons other than lack of efficacy will be excluded from the PP population, but included in the mITT population. Subjects discontinued early for lack of efficacy will be included in the PP population, using LOCF imputation for missing efficacy results. The PP population will be used to compare test and reference products for equivalence.

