5.4. Subject Withdrawal

All subjects are free to withdraw from participation in the study at any time, for any reason, specified or unspecified, and without prejudice to further treatment. The criteria for enrollment are to be followed explicitly. If a subject who does not meet enrollment criteria is inadvertently enrolled, that subject will be withdrawn from the study and the Sponsor or AXIS must be contacted. An exception may be granted in rare circumstances where there is a compelling safety reason to allow the subject to continue. In these rare cases, the PI must obtain documented approval from the Sponsor or designee to allow the subject to continue in the study. Subjects who withdraw themselves or withdrawn by PI for lack of efficacy or Adverse events will be provided free available treatment as per the clinical practice of the PI. PI/ study team need to educate the subjects for completion of study and must make all possible efforts to contact the subject if they do not visit the site as per the schedule within window period.

In addition, study drug will be stopped and subject can be withdrawn from the study in the following circumstances:

- The investigator decides that the subject must be withdrawn
 - Subjects who experience asthma exacerbations that requires treatment with systemic corticosteroids, LABA and high dose ICS's
 - If subject develops a medical condition that requires consistent use of prohibited medication
 - Use of rescue medication more than 600 micrograms per day
 - If FEV1 value is < 45 % on Day 21+ 1
 - The subject is unwilling to continue in the study
 - Violation of criteria listed in the Protocol
 - Noncompliance with Protocol
 - Any treated subject who has an adverse reaction to study medication that threatens his/her well-being if continued in the study
 - If the Investigator decides to stop the treatment
 - The Investigator or the Sponsor, for any reason, decides to stop the study
- Subjects who withdraw from the study early will have early withdrawal procedures performed. Subjects who withdraw from the study will not be replaced.

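### Section 10.2.3 means to keep efficacy failures in the per-protocol equivalence population, but its undefined labels and the 56-dose compliance rule can remove them

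*Protocol*

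**What the plan says.** Protocol section 10.2.3 makes PP the population for the test-versus-reference equivalence comparison. Its first paragraph requires that a subject meet the entry criteria, be compliant with study treatment, either return for the week 4 visit or "discontinue from the study as a treatment failure", and have no major deviation affecting efficacy. Compliant means 75% to 125% of doses.

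Its second paragraph uses another term. On one side, "Subjects discontinued early for reasons other than lack of efficacy will be excluded from the PP population". On the other, "Subjects discontinued early for lack of efficacy will be included in the PP population, using LOCF imputation for missing efficacy results".

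Section 5.4 lists the circumstances in which study drug is stopped and the subject can be withdrawn. Three of them reflect worsening asthma: "Subjects who experience asthma exacerbations that requires treatment with systemic corticosteroids" (the item goes on to LABA and high-dose ICS), "Use of rescue medication more than 600 micrograms per day", and an FEV1 below 45% at the Day 21 visit. They share one list with non-compliance, protocol violation, adverse reaction and unwillingness to continue. None is called treatment failure or lack of efficacy. Section 5.4 does use the second term once, in a sentence on care after withdrawal: "Subjects who withdraw themselves or withdrawn by PI for lack of efficacy or Adverse events will be provided free available treatment".

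Section 9.6 defines compliance as doses administered over doses expected. Its worked example is a subject who stops on day 11 after 18 doses. The denominator stays at 56, giving 32.1%.

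**The concern.** Membership of the equivalence population depends on the recorded reason for stopping, and two features of the text work against the stated intention.

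**Labels.** Neither retaining term is defined. Treatment failure appears only in 10.2.3, and the criteria that would naturally define it carry no label. Exacerbations are described in section 8.6, within the Adverse Events chapter, and 5.4 names lack of efficacy and adverse events as separate reasons. An exacerbation stop recorded as an adverse event is a plausible entry, and 10.2.3 then excludes it.

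**Compliance.** Even a stop correctly labelled as lack of efficacy must pass the 75% rule, and the full-course denominator makes that impossible for most early stops.

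The exclusion depends on outcome. If the test product is weaker, more of its subjects worsen. Removing them raises the test mean more than the reference mean and moves the ratio toward 1, which favours a conclusion of equivalence. Lack of efficacy is also the term that decides in 10.2.2 and 10.4.5 whether baseline is carried forward: "If subject discontinued due to lack of efficacy and does not have a post baseline value". The withdrawal procedures in section 4.7 do not list spirometry, so this affects stops before Visit 4.

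**Working it through.** **1. The plan's own figure.** Section 10.1 gives a reference change of 0.24 L, a CV of 115.5% and 470 PP subjects per active arm. SD = 1.155 × 0.24 = 0.2772 L. The 90% Fieller interval lies within 0.80 to 1.25 when two one-sided 5% tests, on T − 0.80R and 1.25R − T, both reject. Their standard errors are SD × √(1.64/470) and SD × √(2.5625/470). At a true ratio of 1.00 the power is 0.801, matching the stated 0.80. At a true ratio of 0.80 the probability of declaring equivalence is 0.050, as it should be.

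**2. Compliance of an early failure (sections 9.6 and 10.2.3).**
- Doses needed: 0.75 × 56 = 42, which is 21 full days. With the first dose on the morning of Day 15, dose 42 falls on the evening of Day 35.
- Doses before Visit 4, with spirometry before the morning dose: Day 20 gives 5 × 2 = 10, and Day 22 gives 7 × 2 = 14.
- Compliance at a Visit 4 stop: 10/56 = 17.9% to 14/56 = 25.0%, against the 75% floor.

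The FEV1 criterion applies at Visit 4, so a stop then under that criterion is non-compliant by this formula. So is an exacerbation or rescue-use stop before dose 42. Read as compliant AND (returned OR treatment failure), the first paragraph of 10.2.3 excludes subjects whom the second paragraph includes.

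**3. Size, under assumptions.** The protocol gives no treatment-failure rates. The following are assumed:
- 470 per arm before any exclusion.
- Baseline FEV1 mean 67% and SD 10% of predicted, with predicted volume 3.0 L.
- Visit 4 change averaging 0.6 of the final change, with correlation 0.6.
- Exacerbation or rescue stops in 3% of reference subjects, correlated 0, 0.5 or 0.8 with the final change.
- About 2% with FEV1 below 45% at Visit 4, so about 5% efficacy-driven stops in all.

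Probability of declaring equivalence at a true ratio of 0.80:

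| Handling of stops | corr. 0 | 0.5 | 0.8 |
|---|---|---|---|
| All kept with Visit 4 value | 0.04–0.05 | 0.04–0.05 | 0.04–0.05 |
| All three kinds dropped | 0.07 | 0.10 | 0.15 |
| Only exacerbation/rescue stops dropped, 3% | 0.04 | 0.06 | 0.10 |
| Only exacerbation/rescue stops dropped, 2% | 0.04 | 0.05 | 0.08 |

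When all three kinds are dropped, the expected ratio moves from 0.80 to 0.81–0.84.

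**4. Upper bound.** Suppose the stoppers are exactly those below the worst 2%, 3% or 4% point of reference outcomes. Truncating both normal distributions there (means 0.192 and 0.24 L) gives ratios of 0.833, 0.844 and 0.852, and false-equivalence rates of 0.14, 0.18 and 0.23.

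**5. Power cost of keeping them.** In the model of step 3 at a true ratio of 1.00, power is about 0.71–0.78 with stops kept and about 0.80–0.89 with all dropped.

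**The case against.** **This is SAP detail.** Section 10 leaves detailed analysis description to an SAP that is not at hand, and mapping stop reasons to lack of efficacy is commonly done there or at blinded review. The two terms also read naturally as synonyms. This has force against the missing definition taken alone. It does not answer the compliance conflict, because the protocol itself fixes the formula, the denominator and the 75% floor.

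**Nothing directs miscoding.** A reader might infer that following 10.2.3 literally removes everyone whose asthma worsened because of the labels alone. The text does not support that. No section tells the investigator to record an exacerbation as an adverse event, Appendix 6 treats exacerbations under escape criteria, and lack of efficacy is the obvious reason for an FEV1 or rescue-use stop. By the label route, exclusion is possible, mainly for exacerbations. The compliance route is the firmer one.

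**Assignment is blinded.** Section 10.2.3 finalises population assignment before unblinding, and section 10.2 lists exclusions by subject. Membership is therefore not purely a site decision and cannot follow known treatment. This stands, but blinding does not remove a bias that arises because exclusion depends on outcome.

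**The first paragraph could be parsed differently,** with treatment failure as an alternative to compliance as well as to the return visit. That would rescue the intention, but the sentence lists compliance as a separate condition.

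**Conclusion.** The point holds as a defect of drafting with statistical consequences. Section 10.2.3 intends efficacy failures to remain in the equivalence population. The undefined labels leave this to how a stop is recorded, and the 56-dose denominator contradicts it for any failure before 42 doses. The contradiction rests on the protocol's own arithmetic.

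The size of any bias cannot be computed from the documents. With assumed stop rates of a few percent, the false-equivalence rate at a true ratio of 0.80 is about 0.05 to 0.15. The lower part of that range applies if only exacerbation and rescue stops are lost, or if stopping is weakly related to outcome. The 0.14–0.23 figures are an upper bound that requires the stoppers to be exactly the worst outcomes; they should not be read as expected error rates. The 2% rate of increased asthma symptoms at 80–160 mcg/day in the label table of section 1.0 does not settle the matter, since it counts adverse-event reports and not withdrawals.

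**What to change.** - Use one term in 10.2.2, 10.2.3 and 10.4.5. Define it as study drug stopped after randomisation under any of the existing worsening-asthma criteria of 5.4, or for investigator-judged lack of efficacy, whether or not the event is also reported as an adverse event.
- State in 10.2.3 that these subjects stay in PP under the existing carry-forward rules and are exempt from the 56-dose compliance requirement. Alternatively, compute compliance over time on treatment. Reconcile 9.6 and its example with whichever is chosen.
- Record the specific stop criterion on the eCRF discontinuation page and derive the flag from it before unblinding.

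The clinical stopping criteria are unchanged.

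The direct cost is wording in four sections and one eCRF field. The statistical cost is lower equivalence power than if these subjects were dropped. Under the step 3 assumptions it falls below the 80% target, so the sponsor should recheck the section 10.1 simulation with failures retained and decide whether the sample size still suffices.
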